1.7.2 Potential Benefits

There is no direct benefit to study participants beyond a potential benefit to society resulting from improved understanding of investigational vaccines to prevent COVID-19 disease.

Vaccination with ARCT-021, ARCT-154, and ARCT-165 may or may not provide protection against SARS-CoV-2 infection and COVID-19. As the study design includes receipt of vaccination with ARCT-021, ARCT-154, or ARCT-165, if any of these study vaccines are

effective in preventing COVID-19, then participants receiving that study vaccine will have the opportunity to derive clinical benefit.

1.7.3 Overall Risk: Benefit Assessment

This protocol includes measures taken to minimize risks to potential study participants. In addition, the available non-clinical data with ARCT-165 and ARCT-154 and clinical data with ARCT-021 reflect that the self-replicating mRNA vaccine construct is immunogenic and well tolerated. This favorable risk/benefit profile supports evaluation of ARCT-021, ARCT-154, and ARCT-165 in SARS-CoV-2 vaccine-naïve participants as well as in previously SARS-CoV-2- vaccinated participants in this Phase 1/2 clinical study.

2 STUDY OBJECTIVES AND ENDPOINTS

2.1 Primary Objectives and Endpoints

The primary objective(s) and endpoints are presented in [Table 2](#).

Table 2 Primary Objectives and Endpoints

Primary Objectives	Endpoint Description
1. To describe the safety and reactogenicity of 3 investigational SARS-CoV-2 self-amplifying RNA vaccines	
Endpoint 1: Safety will be summarized for each vaccination as the number and percentage of participants with the following:
 
d. Any solicited local or systemic AE collected for 7 days after each study vaccination, which will be assessed by toxicity gradee. Any unsolicited AE collected for 28 days after each study vaccination, which will be assessed by severity and relationship to study vaccinef. Any MAAEs, AEs leading to discontinuation from study vaccine/study withdrawal, or SAEs through Final Visit/ET Visit (Final Visit is defined as 365 days after the last study vaccine dose)
2. To describe the immunogenicity (antibody responses) of 3 investigational SARS-CoV-2 self-amplifying RNA vaccines	
Immunogenicity (antibody responses) will be evaluated after vaccination using the following assays and approaches:
 
Endpoint 2: SARS-CoV-2 neutralizing antibody concentrations by pseudoviral microneutralization assay (ancestral strain, D614G variant, and SARS-CoV-2 Beta variant [as available]). Assay results will be evaluated as follows:
 
a. GMCs at each time point designated in the Schedule of Assessments (Appendix 1 and Appendix 2).b. GMFR from before vaccination to each subsequent time point evaluated after vaccination.c. Proportion of participants achieving ≥ 4-fold rise from before vaccination to each subsequent time point evaluated after vaccination.d. GMC ratio (ARCT-021/ARCT-165, ARCT-165/ARCT-154, and ARCT-021/ARCT-154) measured at all time points evaluated.e. Exploratory: Neutralizing antibody responses to other SARS-CoV-2 variant strains may also be performed and will be described in the SAP. 
Endpoint 3: Binding antibody concentration: IgG to variant-specific SARS-CoV-2 full-length spike, RBD, and N antigens measured by MSD multiplex assay

Table 2 Primary Objectives and Endpoints

Primary Objectives	Endpoint Description
	
(ancestral strain, D614G variant, SARS-CoV-2 Beta variant, as available) will be evaluated as:
 
a. GMCs at each time point designated in the Schedule of Assessments (Appendix 1 and Appendix 2).b. GMFR from before vaccination to each subsequent time point after vaccination.c. Proportion of participants achieving ≥ 4-fold rise from before vaccination to each subsequent time point after vaccination.d. Exploratory: Binding antibody responses to other SARS-CoV-2 variant strains may also be performed and will be described in the SAP.

Abbreviations: AE=adverse event; ET=early termination; GMC=geometric mean concentrations; GMFR=geometric mean fold rise; IgG=immunoglobulin G; MAAE=medically attended adverse events; MSD=Meso Scale Discovery; N=nucleocapsid; RBD=receptor-binding domain; RNA=ribonucleic acid; SAE=serious adverse event; SAP=statistical analysis plan; SARS-CoV-2=severe acute respiratory syndrome coronavirus 2.

2.2 Exploratory Objectives and Endpoints

The exploratory objectives and endpoints are presented in [Table 3](#).

Table 3 Exploratory Objectives and Endpoints

Exploratory Objectives	Endpoint Description
1. To describe and to compare the cell-mediated immune response to different variants of SARS-CoV-2 viruses following vaccination with 3 investigational SARS-CoV-2 self-amplifying RNA vaccines	
Endpoint 1: CMI responses will be measured at designated time points using one or more of the following assays (Appendix 1 and Appendix 2):
 
a. ELISpot (Oxford Immunotec T-spot) assay.b. Intracellular Staining using Flow Cytometry (ICS, Oxford Immunotec)c. Fc effector function: Antibody-mediated cytotoxicity will be measured using surrogate assays measuring CD16 signaling at some or all time points designated in the Schedule of Assessments.d. Additional assays of CMI function may be performed and will be specified in the SAP prior to analysis.

Table 3 Exploratory Objectives and Endpoints

Exploratory Objectives	Endpoint Description
2. To summarize the incidence of COVID-19 cases in enrolled study participants	
Endpoint 2: Virologically confirmed COVID-19 cases occurring after study enrollment will be summarized according to the following:
 
a. Onset within the first 14 days after receipt of the first study vaccinationb. Onset at least 14 days after receipt of the first study vaccinationc. Severity (severe versus non-severe cases) as defined by FDA criteria
3. To provide sera for use for exploratory passive transfer studies in animals	
Endpoint 3: No formal analysis of endpoints will be performed in this study.

Abbreviations: CMI=cell-mediated immunity; COVID-19=Coronavirus disease 2019; ELISpot=enzyme-linked immune absorbent spot; FDA=Food and Drug Administration; RNA=ribonucleic acid; SAP=statistical analysis plan; SARS-CoV-2=severe acute respiratory syndrome coronavirus 2.

3 INVESTIGATIONAL PLAN

3.1 Study Design

This is a randomized, observer-blind, 2-cohort study evaluating the safety, reactogenicity, and immunogenicity of 3 investigational SARS-CoV-2 self-amplifying RNA vaccines. This study is intended for execution in one or more clinical study sites in one or more of the following countries – Singapore, South Africa and the US.

The study will initially enroll approximately 72 adult participants divided into 2 cohorts (A and B) of 36 adult participants each based on previous vaccination status against SARS-CoV-2. Cohort A is further sub-divided into two sub-cohorts which include 12 participants who are seronegative at screening (Sub-cohort A1) and 24 participants who are seropositive at screening (Sub-cohort A2). Based on the review of interim analysis data, the study may be amended to further explore LUNAR SARS-CoV-2 vaccine development. The intended enrollment plan for additional participants will be shared with the applicable health authorities and ethics committee prior to initiation of enrollment.

Within the first cohort (Cohort A), Sub-cohort A1 will include a total of 12 adult participants ≥ 21 to ≤ 65 years of age who have not been previously vaccinated with a SARS-CoV-2 vaccine randomized in a 1:1:1 manner to receive two 5- μ g doses of ARCT-165, ARCT-154, or ARCT-021 on Days 1 and 29. Sub-cohort A2 will include a total of 24 adult participants ≥ 21 to ≤ 65 years of age who have not been previously vaccinated with a SARS-CoV-2 vaccine randomized in a 3:1 manner to receive two 5- μ g doses of ARCT-154 or ARCT-021, respectively, on Days 1 and 29.

The second cohort (Cohort B) will include a total of 36 adult participants ≥ 21 to ≤ 65 years of age who have been previously vaccinated (5 months or longer prior to study enrollment) with the BNT162b2 (Comirnaty) SARS-CoV-2 vaccine randomized in a 1:1:1 manner to receive a single 5- μ g dose of ARCT-165, ARCT-154, or ARCT-021, respectively, on Day 1.

The first 3 participants (sentinel participants) enrolled in each of Sub-cohort A1 and Cohort B will be randomly assigned (1:1:1) to 1 of 3 study vaccines (ARCT-021, ARCT-154, and ARCT-165) administered in a blinded, parallel dosing fashion and the first 4 participants (sentinel participants) enrolled in Sub-cohort A2 will be randomly assigned (3:1) to ARCT-154 or ARCT-021. Safety in each of these sentinel cohort participants (3 participants in Sub-cohort A1 and Cohort B each, and 4 participants in Sub-cohort A2) will be evaluated for 3 days after vaccination. These safety data will also be reviewed by a blinded Safety Review Committee (SRC) prior to the start of dosing of remaining participants in these cohorts.

[figure not shown]
The study will also include the use of pausing and stopping rules that may pause or stop dosing of study vaccination based on any unexpected safety concerns. Further details of the pausing rules are provided in Section [4.2.4](#).

Throughout the study, participants will be regularly assessed for safety using solicited and unsolicited AE collection, concomitant medication, vaccination, and procedure collection, physical examinations, vital signs (VS), body temperature and safety laboratory assessments as specified in the Schedule of Assessments. Participants will also undergo blood sampling for antibody and CMI responses to SARS-CoV-2 vaccines as well as for collection of sera for possible use in non-clinical passive transfer studies. Participants who develop symptoms of

COVID-19 or who are exposed to someone who has been diagnosed with COVID-19 or SARS-CoV-2 infection will undergo testing to determine if the participant has SARS-CoV-2 infection. Safety, immunogenicity, and COVID-19 assessments will be performed through the duration of study participation as specified in the Schedule of Assessments.

The overall design is shown in [Figure 1](#).

Figure 1 ARCT-165-01 Study Schema

Abbreviations: n=number; SARS-CoV-2=severe acute respiratory syndrome coronavirus 2; SRC=Safety Review Committee.

3.1.1 Rationale for Study Design

The SARS-CoV-2 pandemic that was declared in 2020 is continuing to cause global COVID-19 disease in 2021 despite success in developing and emergency use of vaccines directed against the SARS-CoV-2 strain. The control of the disease is complicated by both supply constraints and the emergence of variant strains that may be resistant to vaccination. Additional vaccines that can address priming and boosting vaccination as well as coverage against variants are needed.

This Phase 1/2 study is designed to evaluate the safety, reactogenicity, and immunogenicity of 3 investigational vaccines developed to address the SARS-CoV-2 virus and all developed on the same RNA manufacturing platform: ARCT-021 vaccine, which was developed against the original ancestral strain; ARCT-154 vaccine, which was developed to include the mutation seen in the ancestral strain-D614G variant; and ARCT-165 vaccine, which was developed to include the mutations seen in the SARS-CoV-2 Beta variant strain. These 3 investigational vaccines will be administered to individuals who either may or may not have been previously vaccinated against SARS-CoV-2.

As these study vaccines are built with the same LNP composition and very similar RNA composition to the ARCT-021 vaccine, which has been evaluated in 3 other clinical studies, the starting dose (5 µg) will be based on that previous clinical experience. ARCT-021 is a more pertinent comparator than placebo for the assessment of study objectives as its safety and immunogenicity have been well characterized; also, given the presence of the vaccination campaign in Singapore, South Africa and the US, it is difficult to ethically withhold active vaccine from placebo participants. The introduction of Sub-cohort A2 in protocol v3.0 allows for the further assessment of study vaccines ARCT-154 and ARCT-021 in SARS-CoV-2-vaccine-naïve participants who are seropositive at baseline and will provide valuable safety and immunogenicity data in this important population. Given the stage of the pandemic and high seropositivity rates worldwide amongst unvaccinated populations, understanding the performance of the vaccines and gaining clinical experience in these settings will support ongoing and further clinical development efforts. Preliminary data from the vaccines evaluated in Cohort B of this study highlight that ARCT-154 appears to have broader antibody responses than the ARCT-165 vaccine ([Arcturus 2022b](#), [Arcturus 2022c](#)). For this exploratory study, the shift in randomization will allow for more characterization of the ARCT-154 vaccine immunogenicity in individuals who have signs of prior exposure to one or more SARS-CoV-2 strains. ARCT-021 will be used primarily as a comparator for safety in this randomization scheme.

This study is expected to inform future clinical development planning for SARS-CoV-2 vaccine candidates ARCT-154 and ARCT-165, which are intended for administration to individuals who may or may not have been previously vaccinated.

4 PARTICIPANT SELECTION AND WITHDRAWAL CRITERIA

4.1 Selection of Study Participants

Approximately 72 participants ≥ 21 to ≤ 65 years of age will initially be enrolled (up to a maximum of 144 adults ≥ 21 to ≤ 80 years if additional cohorts are added). Cohort A participants will not have previously received SARS-CoV-2 vaccinations while participants in Cohort B will have received 2 doses of the BNT162b2 SARS-CoV-2 vaccine at least 5 months prior to study enrollment.

Participants who withdraw from the study after randomization may be replaced.

Deviations from the inclusion and exclusion criteria are not allowed because they can potentially jeopardize the scientific integrity of the study, regulatory acceptability, or participant safety. Therefore, adherence to the eligibility criteria as specified in the protocol is essential.

Participants officially enter the Screening Period following documentation of their informed consent either directly or via a legally authorized representative.

Screen failures are individuals who fail to meet all inclusion criteria or who meet at least 1 of the exclusion criteria.

Rescreening will be permitted for the following circumstances:

- Expiry of the Screening Visit window without enrollment for an individual who otherwise appeared eligible for study participation
- Screening safety laboratory assessments may be repeated up to twice if the first value is inconsistent with previously documented laboratory results and subject to the review and approval of the Medical Monitor.

Note: A fever the day before Screening/First Visit does not result in a Screening failure, but it would result in a delay of study vaccine administration.

4.1.1 Inclusion Criteria

Each participant must meet all of the following criteria to be enrolled in this study:

Consent and Compliance

1. Individuals or legally authorized representatives must freely provide consent to study participation.
2. Individuals must agree to comply with all study visits and procedures (including blood, nasopharyngeal swabs, Diary Card completion, receipt of telephone calls from the site, willingness to be available for unscheduled clinic visits).
3. Individuals of childbearing potential that are sexually active in relationship(s) must be willing to adhere to contraceptive requirements. Refer to [Appendix 4](#) (Contraceptive Guidance) for further details.
4. Individuals willing to comply with study prohibitions and refrain from blood donation throughout study participation.

Age and Gender

5. Male, female, or transgender adults ≥ 21 to ≤ 65 years of age (Cohorts A and B) at enrollment.

Type of Participant

6. Cohort B only: Individuals who have received 2 doses of BNT162b2 (Comirnaty) vaccine (5 months or longer prior to study enrollment).
7. Sub-cohort A2 only: Screening SARS-CoV-2 nucleocapsid binding antibody test results that are positive (all countries).
8. Individuals with body mass index of ≥ 18 to ≤ 35 kg/m² at Screening.
9. Females: Must be non-pregnant and non-lactating.

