6.7 Surveillance for SARS-CoV-2 Infection

In concert with the collection of AEs, participants will be interviewed for potential symptoms of COVID-19 disease, recent diagnosis of SARS-CoV-2 infection, and for potential exposure to COVID-19. The assessment of causality and severity for COVID-19 events will be evaluated in accordance with practices for other unsolicited adverse events.

Potential symptoms of COVID-19 disease include, at a minimum, fever or chills, cough, shortness of breath or difficulty breathing, fatigue, muscle or body aches, headache, new loss of taste or smell, sore throat, congestion or runny nose, nausea or vomiting, and diarrhea.

Exposure to COVID-19 is defined as a participant who has had close contact (within 6 feet [2 meters] for a total of 15 minutes or more) to a person with laboratory-confirmed COVID-19 (or clinically compatible illness) or to a person who has tested positive for COVID-19 (laboratory confirmed) but has not had any symptoms.

This is irrespective of whether the person with COVID-19 or the contact was wearing a mask or whether the contact was wearing respiratory personal protective equipment (PPE).

Participants should be reminded to contact the site within 24 hours if experiencing COVID-19-like symptoms or if exposed to a confirmed COVID-19 case.

Evaluation of participants with suspected COVID-19:

6. If a participant reports symptoms of potential COVID-19, an unscheduled clinic visit should occur within 48 hours
 - a. Reported symptoms include at a minimum: fever, chills, cough, shortness of breath or difficulty breathing, fatigue, muscle or body aches, headache, new loss of taste or smell, sore throat, congestion or runny nose, nausea or vomiting, and/or diarrhea.
 - b. An exception to this is if the potential symptoms of COVID-19 are observed within 7 days following study vaccination AND the Investigator determines that these symptoms are more consistent with vaccine adverse reactions and not COVID-19 symptoms.
 - c. If local policy does not allow an unscheduled in-person clinic visit, a RT-PCR or rapid antigen test may be performed and a telemedicine visit will be conducted. Alternatively the site can bring the test kit to point of care for sample collection and perform a telemedicine visit.
7. If a participant reports a potential exposure to COVID-19, an unscheduled clinic visit should be performed within 48 hours

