7.5.4 Immunogenicity Analyses

Analyses will be conducted using the Immunogenicity set as defined for the specific assay under evaluation. Immunogenicity endpoints are described in Section 2 and will be summarized, by study vaccine group and time point, using descriptive statistics. If formal statistical testing is performed, it will be described in the SAP.

The kinetics of immune response following vaccination with each study vaccination will be evaluated in binding, neutralizing antibody responses, and CMI through 365 days after the last vaccination.

Participants who have a nucleocapsid (N) binding antibody test that is positive during the study will be identified, and sensitivity analyses of the immunogenicity data will be conducted with and without participants with this positive test.

A full description of planned analyses for immunogenicity endpoints will be contained in the SAP prior to the time of the intended analysis.

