3.4 Immunogenicity, Safety, and Other Variables

3.4.1 Immunogenicity Variables

3.4.1.1 Primary Immunogenicity Variables

The primary immunogenicity endpoints include:

- SARS-CoV-2 neutralizing antibody titer by pseudoviral microneutralization assay (ancestral strain, D614G variant, and B.1.351 [Beta] variant [as available]) from the PPD Laboratory. Assay results will be evaluated as follows:
 - Geometric mean concentrations (GMCs) at each time point designated in the schedule of assessments;
 - Geometric mean fold rise (GMFR) from baseline (pre-vaccination blood samples drawn Day 1) to each subsequent time point evaluated after vaccination;
 - Proportion of participants achieving ≥ 4 -fold rise in titer from baseline (pre-vaccination blood samples drawn Day 1) to each subsequent time point evaluated after vaccination; and
 - GMC ratio (ARCT-021/ARCT-165, ARCT-165/ARCT-154, and ARCT-021/ARCT-154 where applicable) measured at all time points evaluated.

- Binding antibody titer: Immunoglobulin G (IgG) to variant-specific SARS-CoV-2 full-length spike, receptor-binding domain (RBD), and N antigens measured by Meso Scale Discovery (MSD) multiplex assay from the PPD Laboratory (ancestral strain, D614G variant, and B.1.351 [Beta] variant, as available):
 - Geometric mean concentrations (GMCs) at each time point designated in the schedule of assessments;
 - GMFR from baseline (pre-vaccination blood samples drawn Day 1) to each subsequent time point evaluated after vaccination; and
 - Proportion of participants achieving ≥ 4 -fold rise in GMC from baseline (pre-vaccination blood samples drawn Day 1) to each subsequent time point evaluated after vaccination.

3.4.1.2 *Exploratory Immunogenicity Variables*

The cell-mediated immune responses to different variants of SARS-CoV-2 following vaccination is an exploratory immunogenicity endpoint. It will be measured at designated time points using one or more of the following assays:

- ELISpot (Oxford Immunotec T-spot) assay assessing IFN- γ secreting T cells (spots/ 10^6 PBMCs);
- Intracellular Cytokine Staining (ICS) assay assessing IFN- γ , TNF- α , IL-2, IL-4, IL-5, and IL-13 expressing CD4+ and CD8+ T cells; or
- Fc effector function: Antibody-mediated cytotoxicity will be measured using surrogate assays measuring CD16 signaling at some or all time points designated in the schedule of assessments.

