3.4.3 COVID-19 and SARS CoV-2 Infection Surveillance and Counseling

In concert with the collection of AEs, participants will be interviewed for potential symptoms of COVID-19 disease, recent diagnosis of SARS-CoV-2 infection, and for potential exposure to COVID-19. Potential symptoms of COVID-19 disease include, at a minimum, fever or chills, cough, shortness of breath or difficulty breathing, fatigue, muscle or body aches, headache, new loss of taste or smell, sore throat, congestion or

runny nose, nausea or vomiting, and diarrhea. Exposure to COVID-19 is defined as a participant who has had close contact (within 6 feet [2 meters] for a total of 15 minutes or more) to a person with laboratory-confirmed COVID-19 (or clinically compatible illness) or to a person who has tested positive for COVID-19 (laboratory confirmed) but has not had any symptoms.

Virologically confirmed COVID-19 cases occurring after study enrollment will be categorized by severity as defined by FDA criteria. Virologically confirmed cases are those cases with a positive laboratory test. The assessment of severity per FDA criteria is part of the Safety Review Committee (SRC) meetings, and will be performed for all cases where COVID-19 is confirmed. The assessment of severity per FDA criteria will be limited to confirmed COVID-19 cases, and will not be performed for suspected COVID-19 cases.

Compliance with counseling for long-term follow-up for SARS-CoV-2 infection will be provided for all participants who choose to terminate the study early. Participants will be told to inform the Investigator if they develop symptoms compatible with COVID-19 or a confirmed diagnosis of SARS-CoV-2 infection within 12 months after the last dose of the study vaccine.

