4.5 Immunogenicity Evaluation

4.5.1 Datasets Analyzed

All immunogenicity summaries will be based on the IAS and summaries for key selected assays may be repeated for the FAS. For participants who have a confirmed COVID infection on-study, data will be censored at the last visit prior to their confirmed COVID infection.

A data listing of participants excluded from the IAS, to include the reason for exclusion, will be presented.

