4.8 Statistical/Analytical Issues

4.8.1.1 *Adjustments for Covariates*

There are no planned applications of covariate adjustments; all statistical results are descriptive in nature.

4.8.1.2 *Handling of Dropouts or Missing Data*

No imputations will be performed on missing data for immunogenicity analyses; all analyses will be based on observed data only. Handling of missing adverse event or concomitant medications is described in [Section 4.6.2](#) and [Section 4.6.5.5](#) respectively.

4.8.1.3 *Interim Analyses and Data Monitoring*

There are no interim analyses planned, although an optional interim analysis is permitted by the protocol.

4.8.1.4 *Multicenter Studies*

This is a multicenter study, with approximately 4 sites expected to participate. Immunogenicity data collected from all study sites will be pooled for data analysis. The effect of study site on the analysis results may be explored post-hoc, as needed.

4.8.1.5 *Multiple Comparisons/Multiplicity*

There will be no adjustments for multiple comparisons in the immunogenicity analyses for this study. Results are descriptive in nature and there will be no formal comparisons made among study vaccine groups.

4.8.1.6 *Active-Control Studies Intended to Show Equivalence*

This study does not include an active-control product and is not intended to demonstrate equivalence between any two drug products.

4.8.1.7 *Examination of Subgroups*

Participants who have a nucleocapsid (N) binding antibody test that is positive during the study will be identified, and the immunogenicity analyses may be repeated for participants with and without this positive test, as applicable (for participants who are seronegative at baseline).

4.9 **Determination of Sample Size**

No formal sample size calculation was performed. Based on experience in the ARCT-021-01 study, the size of individual study vaccine groups was considered sufficient to meet the objectives of the study while minimizing unnecessary participant exposure.

4.10 **Changes in the Conduct of the Study or Planned Analyses**

There were no changes to the study conduct or planned analyses identified within the development of this SAP, relative to the descriptions provided within the clinical study protocol.

One clarification to the planned analyses is that the protocol stated that the MNT assay could include the ancestral strain, if available. The ancestral strain was not available and therefore not included as part of the planned analysis.

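### In Sub-cohort A2 a positive N test cannot show new infection, and no rule uses an individual's rise in N IgG in its place, so infections that triggered testing misses count as vaccine response

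*Protocol*

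**What the plan says.** Protocol 4.1.1, criterion 7, sets the A2 entry condition: "Sub-cohort A2 only: Screening SARS-CoV-2 nucleocapsid binding antibody test results that are positive (all countries".

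The plan has two ways of separating infection from vaccine response.

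- **N-test flag.** Protocol 7.5.4 flags anyone whose N test turns out positive on study and requires a repeat analysis: "sensitivity analyses of the immunogenicity data will be conducted with and without participants with this positive test". SAP 4.8.1.7 makes the repeat analysis optional and restricts it: "as applicable (for participants who are seronegative at baseline". SAP 4.10 nevertheless reports no change from the protocol's planned analyses.
- **Censoring.** SAP 4.5.1, for participants with a confirmed infection: "data will be censored at the last visit prior to their confirmed COVID infection". SAP 3.4.3 explains confirmation: "Virologically confirmed cases are those cases with a positive laboratory test". Protocol Appendix 1 marks the SARS-CoV-2 sample at the unscheduled visit only. Testing follows symptoms or reported exposure; for exposure, Protocol 6.7 says "If a participant reports a potential exposure to COVID-19, an unscheduled clinic visit should be performed within 48 hours".

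N IgG is also a quantitative endpoint. SAP 3.4.1.1 lists IgG to full-length spike, "receptor-binding domain (RBD), and N antigens measured by Meso Scale Discovery (MSD) multiplex assay", summarised as GMC, GMFR and the proportion with a ≥4-fold rise from Day 1.

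**The concern.** A yes/no N test is informative about new infection only in someone who starts negative. A2 was added in protocol version 3.0 and is selected for being positive. The amendment summary lists no matching change to 7.5.4, so the flag appears not to have been adapted to this population.

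A2 is 24 of the 36 participants planned for Cohort A, and its stated purpose is to characterise ARCT-154 immunogenicity in people with prior exposure. Antibody response is a primary objective, and its kinetics are followed to 365 days after the last dose. In a descriptive study the GMC, GMFR and ≥4-fold figures are the result. An unrecognised infection between visits raises spike antibody and would make ARCT-154 look more immunogenic or more durable than it is. The visits at Days 119, 209, 299 and 394 are the most exposed, because infections accumulate over follow-up and the vaccine-induced titre may have waned by then.

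**Working it through.** The plan states no power, infection rate or assay-performance figure to reproduce. The check has a logical part and an illustrative part.

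**1. Does each safeguard work in A2?**

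| Safeguard | Source | In A2 |
|---|---|---|
| With/without positive N test | Protocol 7.5.4 | All are N-positive at screening. The 'without' set is essentially empty; only someone who drops below the cut-off on study could enter it |
| Optional N subgroup repeat | SAP 4.8.1.7 | Does not apply; limited to baseline-seronegative participants |
| Censoring at confirmed infection | SAP 4.5.1, 3.4.3 | Works if a swab is taken after symptoms or reported exposure and is positive |
| N IgG GMC, GMFR, ≥4-fold rise from Day 1 | SAP 3.4.1.1 | Computed and tabulated by group; no rule links an individual's rise to that person's spike or neutralising data |

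An infection with no symptoms and no recognised exposure passes through all four rows without being flagged or removed.

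**2. Could an N rise identify it?** By Protocol 1.4 the three replicons encode a replicase and the spike glycoprotein. Vaccination should therefore not raise N IgG, and a rise points to infection. Antibody samples are drawn on Days 1, 15, 29, 43, 57, 119, 209, 299 and 394 (Protocol 6.2.1 and Appendix 1), so the data will exist.

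**3. Who is affected?** 24 randomised 3:1 gives 24 × 3/4 = 18 on ARCT-154 and 24 × 1/4 = 6 on ARCT-021. Sub-cohort A1 adds 12/3 = 4 on ARCT-154, so A2 holds 18 of the 22 planned ARCT-154 recipients in Cohort A.

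**4. How large could the effect be?** Suppose k of n participants have an undetected infection before the visit and each has a titre multiplied by b at that visit. The arm's mean log titre rises by (k/n) × log b, so the GMC is multiplied by b^(k/n). The GMFR is multiplied by the same factor, because the Day 1 value is unchanged. Neither k nor b is in the documents; both are assumed. For ARCT-154 (n = 18):

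| k | b = 4 | b = 8 | b = 16 |
|---|---|---|---|
| 1 | 1.08 | 1.12 | 1.17 |
| 2 | 1.17 | 1.26 | 1.36 |
| 3 | 1.26 | 1.41 | 1.59 |

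For example, 4^(2/18) = 1.17 and 16^(2/18) = 1.36. One participant wrongly counted as a ≥4-fold responder adds 1/18 = 5.6 percentage points, provided that person was not already a responder.

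**5. How plausible is k = 1 or 2?** If the risk of an undetected infection over follow-up were 5%, the expected number among 18 is 0.9 and the chance of at least one is 1 − 0.95^18 = 60%. At 10% the figures are 1.8 and 1 − 0.90^18 = 85%. These risks are also assumptions.

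**The case against.** **The marker is measured.** A reader might infer that A2 has no serological marker of new infection. The documents do not support that: N IgG concentration and its ≥4-fold rise from Day 1 are planned endpoints, and individual results go into listings. This stands. The gap is a missing rule for using the data.

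**Testing is not limited to symptomatic people.** A reader might infer that all asymptomatic infections stay in the A2 results. Every scheduled visit includes an interview about symptoms and exposure, and exposed participants without symptoms are tested. Only infections with no symptoms, no recognised exposure and no outside diagnosis escape. This stands, with one loose end: SAP 4.5.1 does not say whether an asymptomatic positive counts as a confirmed COVID infection for censoring.

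**Criterion 7 and the SAP restriction are not errors.** Studying seropositive people is the purpose of A2, and a positive-N flag belongs in participants who start negative. This stands. What is absent is a substitute for A2.

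**ARCT-021 in A2 is primarily a safety comparator** (Protocol 3.1.1), and no formal comparison is planned. The ARCT-021/ARCT-154 ratio, with six participants on one side, should therefore not carry the argument.

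**The shift is modest against sampling error.** With an assumed log10 SD of 0.3 to 0.6, the planned 95% t-interval at n = 18 spans a factor of about 1.4 to 2.0 either side of the GMC. A factor of 1.17 to 1.36 lies inside that. True, but the shift is a bias in one direction, and the interval does not correct for it.

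**The SAP leaves room.** Its introduction allows amendment for Cohort A before database lock. That permits the repair but does not plan it.

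**Conclusion.** The concern holds as a missing rule. The positive-N flag carries essentially no information about new infection in A2, the SAP's version of the analysis leaves A2 out, and no individual N IgG rise criterion takes its place. Infections missed by symptom- or exposure-triggered testing would be reported as vaccine response, mainly in the ARCT-154 arm at the later visits.

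Two undetected infections among 18 with a 4- to 16-fold boost would multiply the ARCT-154 GMC and GMFR by 1.17 to 1.36. This rests on an assumed infection count, an assumed boost, and the boost persisting in full at the visit analysed. It shows scale and does not predict what happened. The documents do not support reading it as evidence that A2 results are inflated, or that A2 is wholly unprotected. The change is worth making because the existing rule cannot work in this sub-cohort and the repair uses data already being collected.

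**What to change.** Before Cohort A unblinding and database lock, amend SAP 4.8.1.7 and Protocol 7.5.4 as follows:

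- In participants N-positive at Day 1, including A2, a prespecified rise in MSD N IgG identifies probable on-study infection. One option is ≥4-fold from Day 1 or from the preceding scheduled sample; the reference sample and cut should be fixed in advance.
- As a sensitivity analysis, repeat GMC, GMFR, the ≥4-fold proportions and the GMC ratio with that participant's data removed from that visit onward.
- Keep the positivity rule for participants N-negative at baseline.
- State in SAP 4.5.1 whether asymptomatic positive tests trigger censoring, and list the difference from Protocol 7.5.4 in SAP 4.10.

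The cost is wording and one extra set of A2 tables, with no new samples or assays. The rule is imperfect. A 4-fold cut will miss modest rises when baseline N IgG is high, and rises that decay between late visits about 90 days apart. Its sensitivity in people already N-positive cannot be computed from the documents, and some late data drop out of the sensitivity set.
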